6.2 Participant Registration

A written, signed, informed consent form (ICF) and a Health Insurance Portability and Accountability Act (HIPAA) authorization must be obtained before any study-specific assessments are initiated. A copy of the signed ICF will be given to the participant and a copy will be filed in the medical record. The original will be kept on file with the study records.

All patients who are consented will be registered in OnCore®, the UCSF Helen Diller Family Comprehensive Cancer Center Clinical Trial Management System (CTMS). The system is password protected and meets HIPAA requirements.

Each participating site is responsible for OnCore® registration of study participants consented at the site.

6.3 Schedule of Procedures and Observations

6.3.1 **Screening Period**

Pretreatment or Screening Evaluations (Baseline, within 4 weeks prior to study registration unless otherwise specified)

Required screening evaluations include:

- Tumor tissue sample:
 - Patients who have had research tissue procured under an omnibus tissue consent, who are determined to have sufficient fresh, fresh-frozen, and paraffin tissue for biomarker analysis, may substitute the archived tissue and do not need to undergo screening research biopsy provided no interval anti-neoplastic therapy was given.
 - Baseline research biopsy: If no archival tissue is available participants must undergo tissue biopsy at baseline (see below):
 - Examination under anesthesia (EUA) with triple endoscopy is strongly recommended, if not previously performed and/or if an appropriate standard of care for surgical staging. EUA may include direct laryngoscopy, bronchoscopy and esophagoscopy in order to fully evaluate the extent of primary tumor and rule out evidence of a second primary aerodigestive tract tumor. A thorough description of the anatomical extent of the head and neck primary tumor will be detailed by the surgeon in the EUA operative report. Biopsy of the primary tumor for diagnosis, if not already done, will be performed during the EUA according to standard pathologic procedures. Research biopsy of the primary tumor for biomarker studies during the EUA is required if no archival tissue is available. Alternately, patients for whom an in-office biopsy with local anesthesia is feasible may have the baseline research biopsy performed in the outpatient office of the otolaryngologist or head and neck surgeon.
 - Tissue for biomarker analysis will be processed according to procedures described in Appendix 5.

Phase 2 - Ruxolitinib Page 37 of 67

Protocol CC# 16201

- Blood collection. The patient is required to undergo blood collection for biomarker assessment. For logistical purposes, research labs may be drawn simultaneous with blood labs required for standard clinical management.
 - Blood for biomarker analysis will be processed according to procedures described in Appendix 5.
- History and physical examination, to include surgical and medical evaluation, within 8
 weeks prior to study registration, including a careful description of the location and
 extent of the primary lesion and nodal spread. Fiberoptic
 nasopharyngoscopy/laryngoscopy is recommended, unless fiberoptic exam is deemed
 unnecessary by the treating surgeon.
- Vital signs, weight, height within 8 weeks prior to study registration
- ECOG Performance Status within 8 weeks prior to study registration
- Laboratory studies including CBC with differential (to include total white blood cell count, absolute neutrophil count, hemoglobin, hematocrit and platelets), serum chemistries (to include sodium, potassium, chloride, carbon dioxide, BUN, creatinine, glucose, magnesium and calcium), liver function tests (LFTs; to include total bilirubin, AST, ALT, total protein, albumin and alkaline phosphatase), coagulation studies (PT/INR and PTT), and C-reactive protein (CRP).
- Negative serum pregnancy test within 4 weeks of study registration in WOCBP. Note, the clinical research coordinator or treating investigator will document an additional negative pregnancy test within 72 hours of starting ruxolitinib treatment.
- Cross-sectional radiologic evaluation within 6 weeks of study registration (within 4 weeks is preferred). The minimum cross-sectional evaluation is a diagnostic, contrasted computed tomography (CT) scan of the neck. PET/CT is the preferred modality, provided it includes a diagnostic, contrasted CT scan of the neck however is not mandatory. For patients with severe allergy to iodinated contrast dye despite premedication, or in the case of physician preference, neck MRI may be substituted. If MRI is used for baseline imaging, it should also be used for response assessment (post-treatment, pre-surgical imaging). This is standard of care for baseline assessment. The post treatment assessment is research.
- EKG. The standard of care EKG performed for pre-surgical evaluation should be used. EKGs performed within 12 weeks prior to study registration may be substituted, provided the patient has experienced no interval cardiac event.

6.3.2 Treatment Period

Days 1-28; **NOTE** ruxolitinib treatment is planned for 14-21 days, however may be administered up to 28 days if required for logistical/scheduling purposes.

6.3.2.1 **Day 1**

Ruxolitinib will be administered at the FDA-approved dose in myelofibrosis, as determined by baseline platelet count: 1) Patients with a platelet count ≥ 200,000 will take 20 mg bid (four 5mg tablets in the morning and four 5mg tablets in the evening); 2) participants with a platelet count ≥ 150,000 and < 200,000 will take 15 mg bid (three 5 mg tablets in the morning and three 5 mg tablets in the evening). Ruxolitinib will be discontinued on the day of surgical resection (following the morning dose). If surgery is delayed, the study drug may be continued until surgery, for a

Phase 2 - Ruxolitinib Page 38 of 67

Protocol CC# 16201

maximum of 28 days. Fourteen days is the minimum required treatment for a patient to be considered evaluable. The interval between the last dose of ruxolitinib and surgery will be 2-24 hours.

Ruxolitinib will be dispensed as 5mg tablets. Participants with a platelet count \geq 200,000 will take 20 mg bid (four 5mg tablets in the morning and four 5mg tablets in the evening). Participants with a platelet count \geq 150,000 and < 200,000 will take 15 mg bid (three 5 mg tablets in the morning and three 5 mg tablets in the evening).

Participants will be asked to indicate on a drug diary (see Appendix 4) when doses of study drug are taken in order to monitor for compliance. Participants may also use the drug diary for notations on side effects and other treatment related events.

6.3.2.2 Day 9-28 (inclusive of day of surgery)

Post-treatment, pre-surgical

NOTE: all efforts should be made to schedule these evaluations on the day prior to or the day of surgery, however a 5 day window is provided for logistical purposes.

- History and Physical Examination (Post-treatment, Pre-operative): Participants will be evaluated by history and physical examination by the treating physician within 5 days prior to planned surgery (including vital signs, weight, performance status). This visit will also include toxicity and compliance assessment. Compliance as evidenced by pill count and patient drug diary will be assessed. For logistical convenience, this visit may be scheduled in conjunction with blood collection and imaging as specified below. NOTE: Participants will continue to take ruxolitinib until the morning of planned surgery. If surgery is delayed, participants will continue to take ruxolitinib and this pre-operative history and physical examination does not need to be repeated.
- Blood Collection (Clinical and Research Blood): Participants will undergo repeat CBC with differential, serum chemistries, LFTs, coagulation studies and C-reactive protein within 5 days prior to planned surgery. Research blood will be drawn simultaneously with these standard pre-operative labs. NOTE: Participants will continue to take ruxolitinib until the morning of planned surgery. If surgery is delayed, participants will continue to take ruxolitinib and these pre-operative blood tests do not need to be repeated.
- Cross-sectional Imaging for Tumor Measurements (Research): Participants will undergo
 a repeat diagnostic CT scan of the neck with IV contrast within 5 days prior to planned
 surgery. If a neck MRI was performed in lieu of CT scan at baseline, then a MRI should
 be substituted at response assessment. NOTE: Participants will continue to take
 ruxolitinib until the morning of planned surgery. If surgery is delayed, participants will
 continue to take ruxolitinib and this pre-operative imaging does not need to be repeated.

NOTE: in the event that a patient lacks a CT-measurable primary tumor or metastatic lymph node, measurable disease may be established by caliper measurement of an oral cavity or oropharyngeal tumor (≥ 1 centimeter). In this case, caliper measurement should be repeated and documented within 5 days prior to planned surgery, as a substitute for cross-sectional imaging.

Phase 2 - Ruxolitinib Page 39 of 67

Version date: 03-22-2023 Protocol CC# 16201

6.3.2.3 Surgery (Occurring Between Days 14-28, Inclusive)

The nature of complete resection of the primary head and neck tumor, type of reconstruction, and levels of nodes to be dissected will be determined by the treating surgeon. Prior to surgery, dental evaluation is recommended, to allow for any necessary dental extractions to be planned in conjunction with surgery. Consultations with a Nutritionist and Speech and Language Pathologist are strongly recommended prior to surgery and as ongoing support. Placement of a nasogastric (e.g. Dobhoff) or gastrostomy feeding tube is at the discretion of the participant and the study physicians. Following 14-21 days (+ 7 days if required for logistical and scheduling purposes) of treatment prior to participant's scheduled surgery, a surgeon will resect the participant's tumor (days 14-28). Part of the tumor specimen will be sent to the research laboratory for mandatory biomarker analyses. If surgery is unexpectedly cancelled, the patient will be removed from the study unless the primary tumor is accessible for in-office biopsy in the judgment of the surgeon-investigator, in which case a tumor biopsy may be substituted for the operative specimen. Tissue collection procedures are described in Section 9.0.

6.3.2.4 **Post-operative therapy**

After surgery, participants may receive adjuvant radiation or radiation plus chemotherapy in accordance with appropriate standards, as determined by the participant's treating physicians.

6.3.3 End-of-Treatment/Final Study Visit Procedures

A standard history and physical examination and blood tests as clinically indicated (CBC, chemistries, liver function tests in accordance with investigator judgment) will be performed 4 weeks (+/- 2 week) and 12 weeks (+/- 4 weeks) post-surgery. Additional non-protocol visits may occur during the 12-week post-operative period as deemed clinically necessary. Patients will be referred for adjuvant chemotherapy and radiation per standard of care, based upon pathologic findings. Once the first 12 weeks of follow-up have been completed, study follow-up will be discontinued and participants will continue standard treatment and surveillance in accordance with national guidelines.

The standard post-operative visit which occurs 12 weeks post-op (+/- 4 weeks) will be considered the "final study visit."

Post-Therapy Radiologic Evaluation

Within 6 weeks prior to registration (within 4 weeks preferred), and again within the 5 days prior to planned surgery, patients will undergo cross-sectional radiological evaluation using diagnostic contrasted CT, PET/CT (with diagnostic contrasted CT), or MRI of regions with radiologically or clinically identifiable tumor. The minimum cross-sectional evaluation is a diagnostic, contrasted computed tomography (CT) scan of the neck. PET/CT is the preferred modality, **provided it includes a diagnostic, contrasted CT scan of the neck** – however is not mandatory. For patients with severe allergy to iodinated contrast dye despite premedication, or in the case of physician preference, neck MRI may be substituted. The pre- and post-treatment imaging modality should be the same, i.e. if MRI was used at study entry, it should be used at the post-treatment, pre-surgical assessment. Modified Response Evaluation Criteria in Solid Tumors version 1.1 (RECIST v1.1)³⁷ criteria will be used to establish target lesions.

NOTE: in the event that a patient lacks a CT-measurable primary tumor or metastatic lymph node, measurable disease may also be established by caliper measurement of an oral cavity or

Phase 2 - Ruxolitinib Page 40 of 67

oropharyngeal tumor (≥ 1 centimeter). In this case, caliper measurement should be repeated within 5 days prior to planned surgery.

6.4 Usage of Concurrent/Concomitant Medications

6.4.1 **Dietary Restrictions**

Patients will be instructed to avoid grapefruit or grapefruit juice, starfruit, or Seville oranges.

6.4.2 Prohibited Medications

Strong CYP3A4 inhibitors. For eligibility, patients must discontinue drug 7 days prior to starting ruxolitinib, including but not limited to boceprevir, clarithromycin, conivaptam, indinavir, itraconazle, ketoconazole, lopinavir, mibefradil, nefazodone, nelfinavir, posaconazole, ritonavir, saquinavir, telaprevir, telithromycin, or voriconazole.

7 Reporting and Documentation of Results

7.1 Evaluation of Efficacy: Antitumor Effect – Solid Tumors

Response and progression in this study will be evaluated using the new international criteria proposed by the Response Evaluation Criteria in Solid Tumors (RECIST) Committee [JNCI 92(3):205-216, 2000]. Changes in only the largest diameter (unidimensional measurement) of the tumor lesions are used in the RECIST v1.1 criteria (or International Workshop on Chronic Lymphocytic Leukemia [IWCLL]).

7.1.1 **Definitions**

Evaluable for toxicity

All patients will be evaluable for toxicity from the time of their first treatment with the study drug.

Evaluable for objective response

Only those patients who have measurable disease present at baseline, have received at least one cycle of therapy, and have had their disease re-evaluated will be considered evaluable for response. These patients will have their response classified according to the definitions stated below. (Note: Patients who exhibit objective disease progression prior to the end of Cycle 1 will also be considered evaluable.)

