Duration of study	The study will reach completion 24 months from the time the study opens to accrual.		
Study Drugs	Ruxolitinib, JAKAFI®, INCB018424 (JAK 1/2 inhibitor) 20mg (or 15mg) PO BID.		
Safety Assessments	The safety of this window intervention will be reported descriptively, including tabulation of toxicities according to NCI CTCAE v.4, surgical complications, and length of hospital stay.		
Efficacy Assessments	Efficacy of neoadjuvant ruxolitinib in patients with operable HNSCC as determined by quantitative ΔT umor size reflective of a 35% reduction.		

Phase 2 - Ruxolitinib Page 4 of 67

List of Abbreviations

AE adverse event

AUC area under the curve BUN blood urea nitrogen

CBC complete blood cell (count)

CR complete response

CRC Clinical Research Coordinator

CRF case report form CSF cerebral spinal fluid

CT computerized tomography

CTCEA Common Terminology Criteria for Adverse Events

CTEP Cancer Therapy Evaluation Program
CTMS Clinical Trial Management System

DFS disease-free survival

DSMC Data and Safety Monitoring Committee

DSMP Data and Safety Monitoring Plan

ECOG Eastern Cooperative Oncology Group

FDA Food and Drug Administration

GCP Good Clinical Practice

HDFCCC Helen Diller Family Comprehensive Cancer Center

HGB hemoglobin

ICH International Conference on Harmonization

IND investigational new drug application

IRB Institutional Review Board

IV intravenous

MedDRA Medical Dictionary for Regulatory Activities

MRI magnetic resonance imaging
MTD maximum tolerated dose
ORR overall response rate
PD disease progression
PK pharmacokinetics

PO Per os (by mouth, orally)

PR partial response

PRC Protocol Review Committee (UCSF)

QOL Quality of Life

RBC red blood cell (count)

SD stable disease

[figure not shown]
WBC white blood cell (count)

Phase 2 - Ruxolitinib Page 5 of 67

Table of Contents

Pro	tocol	Signature Page	2
		Signature Page – Participating Sites	
Abs	stract	4	
List	of A	obreviations	5
		Contents	
1		roduction	
ı			
	1.1	Background on Indication	
	1.2	Background on RuxolitinibRationale for the Proposed Study	
	1.3	Correlative Biomarker Analysis	
	1.7	1.4.1 Primary Analysis	

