2.2 Secondary Objectives

- To assess preliminary efficacy of neoadjuvant ruxolitinib in patients with operable HNSCC as determined by quantitative ΔTumor size
- To describe the tolerability of brief neoadjuvant exposure to ruxolitinib
- To assess the effect of ruxolitinib on the tumoral Ki-67 proliferation index
- To evaluate additional candidate biomarkers of ruxolitinib response or resistance in HNSCC patients as determined by quantitative ΔTumor size, including:
 - Baseline activation and/or modulation of additional JAK/STAT3 signaling pathway proteins
 - o Baseline SHP-2 overexpression
 - Reverse-phase protein array (RPPA) will be conducted on paired pre- and posttreatment tissue as a source of unbiased biomarker discovery

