4.4 Packaging and Labeling of Study Drugs

Drugs will be packaged and labeled per UCSF institutional standards, adhering to applicable local and federal laws.

5 Treatment Plan

5.1 **Dosage and Administration**

Treatment will be administered on an outpatient basis.

Table 5.1 Regimen Description

Study Drug	Dose	Route	Schedule	Cycle Length
Ruxolitinib	20mg or 15mg dependent on baseline	РО	BID	Pre-operative window (14-21 days) or up to 28 days for delayed
	platelet count			surgery

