- If participants experience any grade 3-4 ruxolitinib-related non-hematologic toxicities in the neo-adjuvant window, the study drug will be discontinued and they will be removed from the study. (Exception: Patients with asymptomatic grade 3 electrolyte abnormalities manageable with repletion) Patients may also be removed from study for intolerable non-hematologic toxicities of any grade, which persist despite optimal medical management.
- If participants experience grade ≥ 3 thrombocytopenia or neutropenia, ruxolitinib will be discontinued and they will be removed from the study.
- Grade 3 anemia does not require discontinuation from protocol. Patients may be transfused per discretion of the treating physicians.
- For mild or moderate (grade 1 or 2) side effects that are difficult to tolerate, treatment
 may be held for up to 1 week. Treatment may be resumed at the same dose, if there is
 improvement by at least one grade. Dose delays more than 1 week will not be permitted.
 If treatment is restarted, study physicians should aim for at least 3 days of ruxolitinib
 exposure prior to planned surgery.

In two Phase 3 clinical studies of ruxolitinib in myelofibrosis, the median time to onset of first CTCAE grade two or higher anemia was 6 weeks, and approximately 8 weeks until onset of grade 3 or 4 thrombocytopenia. In nearly all cases, ruxolitinib-induced anemia and thrombocytopenia could be reversed with dose reduction or interruption; occasionally red blood cell or platelet transfusions were required. Thus, given the short 2-3 weeks of treatment during this study, it is expected that few, if any, participants will develop hematologic abnormalities. Moreover, participants in the current study do not have a primary bone marrow malignancy which is the target of ruxolitinib and thus predisposes to hematologic toxicity. Any participants that experience anemia or thrombocytopenia may be transfused if deemed necessary by the treating physician.

Although clinically significant hematologic and non-hematologic toxicity is unexpected during the 14-21 days of protocol treatment in patients with operable HNSCC, a continuous monitoring rule for excess toxicity will be instituted. Please see Section 5.6 below.

5.6 **Monitoring and Toxicity Management**

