8.3 Interim Analyses and Stopping Rules

This is an open label biomarkers study. No interim analysis is planned.

8.4 **Analyses Plans**

8.4.1 **Analysis Populations**

Safety Population

The safety population will include all enrolled patients who receive at least one dose of ruxolitinib and have the potential to complete pharmacodynamics biomarkers assessments at baseline and the end of study treatment window. Although the risk from specimen collections for biomarker assessment is limited and low, all patients will be evaluable for toxicity and safety assessment of ruxolitinib. Patients who are determined ineligible after enrollment or who are not evaluable for safety analysis (e.g. due to withdrawal of consent or failure of specimens collection as not related to tumor progression and not treatment-related toxicity) will be replaced (see section 8.2.2 for details).

Efficacy Population

The efficacy population for the primary endpoint of 35% or greater reduction in tumor size will include all enrolled patients who have measurable disease present at baseline and have completed tumor assessment at the end of study window. Patients who are determined ineligible after enrollment or who are not evaluable for safety analysis (e.g. due to withdrawal of consent or failure of specimens collection as not related to tumor progression and not treatment-related toxicity) will be replaced (see section 8.2.2 for details).

Phase 2 - Ruxolitinib Page 50 of 67

Version date: 03-22-2023 Protocol CC# 16201

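### Any responder proportion is defined over assessed patients only; treated patients without a second tumor assessment drop out, and no all-treated figure is planned beside it

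*Combined protocol and SAP*

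**What the plan says.** Preliminary efficacy is a secondary objective in Section 2.2 ("To assess preliminary efficacy of neoadjuvant ruxolitinib in patients with operable HNSCC"), judged by quantitative change in tumor size. The Efficacy Assessments row of the Abstract ties efficacy to a change "reflective of a 35% reduction". Section 2.3.2 uses net tumor measurements to determine response, and Section 8.4.3 reports categorical variables as counts and percentages.

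Four places say who is evaluable:

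- **Section 8.4.1, Efficacy Population**, written for the 35% endpoint, will "include all enrolled patients who have measurable disease present at baseline and have completed tumor assessment at the end of study window". It sets no minimum exposure.
- **Section 7.1.1**, written for RECIST response, rules that only patients with baseline measurable disease who "have received at least one cycle of therapy, and have had their disease re-evaluated will be considered evaluable for response". It adds an exception: "Patients who exhibit objective disease progression prior to the end of Cycle 1 will also be considered evaluable". Table 5.1 gives the cycle length as the whole treatment period: "Pre-operative window (14-21 days) or up to 28 days for delayed" surgery.
- **Section 3.5.1** keeps a discontinued patient evaluable given screening tissue, at least 14 days of drug and a response assessment.
- **Section 6.3.2.1** makes 14 days of treatment the minimum for evaluability.

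On early stopping, Section 5.5 says of grade 3 or worse thrombocytopenia or neutropenia that "ruxolitinib will be discontinued and they will be removed from the study". It treats related grade 3-4 non-hematologic toxicity the same way, with one electrolyte exception. The study calendar and Section 6.3.2.2 schedule repeat imaging only within 5 days before planned surgery. Section 8.2.2 enrolls replacements for patients without tumor assessments.

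**The concern.** In a single-arm, open-label study the denominator decides what an activity figure means. A responder percentage among patients who reached the pre-surgical assessment describes those patients. It is likely to be read as the activity of neoadjuvant ruxolitinib in everyone who started it. Patients who stop for toxicity, withdraw or are removed for non-compliance (Section 3.4) are the ones most likely to miss the only scheduled repeat assessment. No section counts them as non-responders or gives a second figure that includes them.

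The four evaluability rules also differ, so one patient can be in for one purpose and out for another. Someone who progresses early and has no end-of-window assessment is evaluable under 7.1.1 but falls outside 8.4.1. Someone who stops before day 14 but is measured at the end of the window meets 8.4.1 but not 6.3.2.1.

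What is at stake is the reading of a secondary efficacy figure. No sample-size calculation, stopping rule or primary test depends on it.

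**Working it through.** **Is there a planned figure to reproduce?** No. The documents give no expected, null or target response rate. The 35% is the shrinkage that makes a patient a responder in the supportive comparisons of Section 8.4.2. What can be calculated is how far the choice of denominator moves a responder proportion.

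**Inputs from the plan.** Section 5.2 gives a beta prior for treatment-related discontinuation with a = 1 and b = 9. Its mean is a/(a+b) = 1/10 = 10%, which reproduces the stated 10%. Section 5.2 also states an approximate 80% mid-range of 0 to 22%, and an upper bound of 33%.

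**Assumption.** Patients who discontinue for toxicity have no second tumor assessment, so d, the fraction unassessed, equals the discontinuation rate. The plan does not say this. It follows from the imaging schedule if no other scan is done.

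**Formula.** Let p_a be the responder proportion among assessed patients and p_u the unknown proportion among unassessed patients. Then

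all-treated proportion = (1-d) × p_a + d × p_u.

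Counting unassessed patients as non-responders sets p_u = 0, so

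assessed-only / all-treated = 1/(1-d).

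| d | Source | 1/(1-d) |
|---|---|---|
| 10% | prior mean, 5.2 | 1/0.90 = 1.11 |
| 22% | top of prior mid-range, 5.2 | 1/0.78 = 1.28 |
| 33% | upper bound, 5.2 | 1/0.67 = 1.49 |

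**Illustration.** Assume 5 responders among 23 assessed patients. Neither number is a plan figure for response; 23 is borrowed only for scale. The assessed-only proportion is 5/23 = 21.7%. The all-treated proportion is 21.7% × 0.90 = 19.6% at d = 10%, and 21.7% × 0.67 = 14.6% at d = 33%. With no responders, both proportions are 0%.

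**Direction.** The ratio is at or above 1 because of the convention p_u = 0. If unassessed patients responded as often as assessed ones (p_u = p_a), the two proportions would agree.

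**The case against.** The strongest reply is that this is a biomarker study. Its primary endpoint is continuous percent change (2.3.1), and its primary analyses are five Spearman correlations (8.4.2). The responder split is labelled supportive and exploratory, the counts-and-percentages wording in 8.4.3 is generic, and no section expressly plans a response rate with a confidence interval. That stands, and it limits the importance of the point. It does not remove it: 8.4.1 builds a population for the 35% endpoint and even calls that endpoint primary, and with the Abstract and Section 2.2 this makes a responder percentage an expected output.

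Four stronger readings are tempting, and the documents do not support them:

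- **That a 35% response rate is inflated.** The 35% is a fixed cut-off for shrinkage and cannot be inflated.
- **That every early stopper is lost, or that a full cycle is needed for the 35% endpoint.** The one-cycle condition is in 7.1.1, which leads to RECIST categories with a 30% threshold for partial response. Section 8.4.1 has no such condition, and 7.1.1 keeps early progressors.
- **That all toxicity stops are replaced.** Section 8.2.2 replaces patients without assessments, but the examples in 8.4.1 are losses unrelated to progression or treatment toxicity. The position is unclear.
- **That the proportion could nearly double, because 45 are accrued for 23 evaluable (45/23 = 1.96).** The 23 are biomarker-evaluable and the 45 are accrued. Patients lost for poor tissue may have both scans, so this ratio compares different populations.

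Two further points stand. That early stoppers lack a second scan is an inference: Section 3.5.1 asks that they be seen if possible. And the plan expects little hematologic toxicity in so short a window (4.1.1, 5.5), so toxicity alone may remove few patients. Withdrawal and non-compliance would add to d by an amount the plan does not give.

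**Conclusion.** The point holds for any responder proportion, whether the 35% endpoint or a RECIST category. Treated patients without a second assessment leave the denominator, and no all-treated figure is described. With unassessed patients counted as non-responders, the assessed-only proportion is at or above the all-treated one, by a factor of about 1.11 if 10% are unassessed and 1.49 if 33% are. Those factors assume that toxicity discontinuations are the only losses and that none of these patients has a second scan.

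A reader might infer that the assessed-only figure must overstate the true activity. The documents do not show that, because the response of unassessed patients is unknown; this is the reason to show both proportions. The primary correlations, their alpha allocation and the sample size do not depend on this denominator. It is a worthwhile, low-cost correction to a secondary analysis.

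**What to change.** In Sections 8.4.1 and 7.1.1, state that the proportion with a reduction of 35% or more, and any RECIST response proportion, is reported over all eligible patients with baseline measurable disease who took at least one dose. Count patients without a second tumor assessment as non-responders, and list the reasons for each missing assessment. Show the assessed-only proportion beside it as supportive.

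Reconcile the evaluability rules in 3.5.1, 6.3.2.1, 7.1.1 and 8.4.1, so that each analysis has one stated population and early progressors are handled the same way in both response definitions. State in 8.2.2 and 8.4.1 whether patients who stop for toxicity are replaced. Leave the five Spearman correlations as they are.

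The cost is a wording change, one extra table line and a somewhat less favourable secondary figure. It needs no additional patients or scans. Section 7.2 already uses an at-least-one-dose set for safety, so the denominator is available.
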